**Future use:**

All the samples remaining will be stored at the CRN unit/Emory hospital until further notice. The PI will decide when to destroy the samples. All the data and materials of this project (including samples, specimens, behavioral results, brain function, physiology and other) will be used only by the PI ([name]) or with her permission for future analysis, future studies etc. If the PI ([name]) leaves Emory, she would like to have access to all the samples and data for future studies. Any future study/collaboration at Emory or other locations using any data or materials

that were collected under this protocol (genetics, clinical, behavior, brain, etc) is possible only after permission of [name].

## **Participant selection:**

50 ASD between the ages of 18 and 45 will participate in this study. 30 healthy controls who are matched by IQ, race, ethnicity and age will also participate in this study. All participants are males.

Healthy subjects will only receive placebo spray. Healthy subjects will be told that they might receive placebo or oxytocin spray (one of the 3 doses). Healthy subjects will participate in one visit during which they complete questionnaires, behavioral tasks, clinical interview and training on the different tasks that they will be doing inside the MRI scanner. They will get a physical, vital signs, blood draws, placebo spray, MRI scan (including all the tasks that are described above) and behavioral tasks after the MRI scan.

ASD subjects will participate in a pre-clinical visit and will perform all the tasks and procedures that are described above. They will also participate in 4 clinical visits that will include treatment intake (syntocinon spray 8IU, 24IU, 48IU and placebo), blood draws, vital signs, MRI scan, behavioral tasks and questionnaires (see below the procedure for more details). It is a placebo-controlled randomized clinical trial, double-blind and within subject design.

Subjects will have normal or corrected-to-normal (with contact lenses) visual acuity of 20/40. MRI-compatible glasses are available for those who wear glasses rather than contact lenses. A medical history will be obtained and reviewed by the study physician or study nurse practitioner, including information about prescription and non-prescription medications.

### Inclusion/exclusion criteria for ASD subjects:

Given that the inclusion criteria list and the screening will be first conducted during the first pre-clinical visit (by [name] or staff and not by nurse practitioner), the experimenter will contact physician [name] or [name] or the nurse practitioner in case there were some doubts.

The nurse practitioner will conduct this screening again during the first clinical visit to make sure that the entire subject meets the criteria of inclusion and exclusion.

### Inclusion:

- Sex males (we are excluding women for this present study given the difficulty to find the same number of women with ASD. Autism is found in men 4 times more than in women as based on CDC epidemiological studies). Also, only male will be included to minimize possible side effects of oxytocin administration that can be related to uterine contractions and lactation in females and to minimize confounding factors that can arise from hormonal interactions with estrogen in women. We are including male sex which means that a gender male person who was born as a woman is not considered part of the inclusion criteria.

- Age: between 18 and 45 years old.
- Have an ASD diagnosis based on the ADOS and ADI criteria, gold standards of research-based autism diagnosis.
- Not color blind (some of the behavioral tasks inside the scanner require detection of color)
- IQ>70
- Normal or corrected-to-normal vision

Exclusion:

- Recent occurrence of seizures (past 5 years) (lot of patients with autism have seizures when they were young and these seizures never re-appear and do not provide a risk for subjects in this study).
- Brain damage or head trauma (can be included at discretion of PI and sponsor)
- Cardiovascular disease
- Presence of a severe medical problem
- Severe mental retardation
- Alcoholism or substance abuse
- Asthma (can be included at the discretion of study physician/nurse practitioner if episodes are infrequent and no active problems at time of the study)
- Migraine headaches (at the discretion of the nurse practitioner or the study physician)
- Claustrophobia (at discretion of study physician/designee/PI)
- Pacemakers, cochlear implants, surgical clips or metal fragments

In the general form, we will take note of any comorbid psychiatric disorder, current medications, current medical problems such as diabetes, migraines and take these factors as covariates in our analysis. We will also take a note of the date of last event and the frequency. We want to try to include as many patients with ASD as possible to represent at best the general population with high functioning autism.

Those who are on medication, we do not exclude them from the study but ask them to continue their treatment as normal.

Inclusion/exclusion criteria for healthy subjects:

Inclusion:

- Sex males between 18 and 45 years old (given that they should be controls for ASD subjects)
- Matched to ASD group
- Not color blind
- IQ > 70

Exclusion:

- History of seizures (past 5 years)
- Neurological disorder

- Current psychiatric disorder
- Previous psychiatric disorder (can be included at discretion of PI). If the date of the last episode is more than one year ago then the PI will include him. If the date of the last episode dates to less than a year, at discretion of PI).
- Head trauma (can be included at discretion of PI)
- Alcoholism or substance abuse
- Cardiovascular disease
- Asthma (can be included at the discretion of study physician/nurse practitioner if episodes are infrequent and no active problems at time of the study)
- Migraine (at the discretion of the nurse practitioner or the study physician)
- Claustrophobia (at discretion of study physician/designee/PI)
- Presence of a severe medical problem
- Severe mental retardation
- Pacemakers, cochlear implants, surgical clips or metal fragments

Given that midway of the study, we had trouble recruiting healthy subjects that are matched with ASD, we asked to add another group of healthy subjects with more selective criteria of inclusion.

We are adding Caucasian as a criterion of inclusion and IQ within the range of 70 and 115.

Of note, given that healthy subjects will not be evaluated by a NP or study physician, the PI and the coordinator will rely on the self-report of these healthy subjects. They will sign the inclusion criteria document.

Subjects will be studied only if they pass the Society of Magnetic Resonance Imaging standardized MRI screening protocol (exclusions for ferrous metal in any part of body, such as pacemakers, cochlear implants, surgical clips or metal fragments, serious medical conditions). Subjects with claustrophobia will be excluded at the discretion of the PI based on consultation with the subject. Subjects with claustrophobia will be carefully monitored and reminded that they are free to withdraw from the study at any time. Subjects who report a history of asthma or migraine headaches will be included at the discretion of the study physician or study nurse practitioner only if episodes are infrequent; there are no active problems at the time of the study. Subjects with a history of head trauma or psychiatric illness will be included at the discretion of the PI. Any cognitive consequence of head injury could be taken into account during the decision.

Subjects will be asked to refrain from use of caffeinated drinks or tobacco for at least 12 hours prior the blood pressure and heart rate measurement.

Given that this project is the continuity of the previous IRB protocol 64623, we will contact healthy subjects and patients with autism that were already recruited in this previous protocol. We are planning to contact those who gave us approval to be contacted (in the consent form). We will go through the screening process (see above for more details) over the phone with the patient and family member if necessary and make sure he is interested and he is eligible for the study. The study coordinator will then schedule them for the first pre-clinical visit.

If a subject withdraws from the study, we will prepare a note to file (and put it in the regulatory binder) and report to the IRB during the continuing review.

We expect to recruit at least 30 patients with autism and 20 healthy controls. We expect a drop off of patients with ASD given that they need to come for 5 visits.

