### **Healthy subjects screening:**

Given that the healthy group of males should match patients with ASD on age, sex and intellectual quotient (IQ), we will first contact patients (from the data base of the previous protocol 64623) and see who is interested and eligible before selecting the matching healthy men controls. We will select healthy participants who already participated in our previous research study (64623). We will use the information collected in project #64623 to match their IQ and age. We will contact participants who agreed to be contacted in the future studies in the consent form of protocol 64623. We will contact healthy subjects by phone and/or email (again from the data base of 64623) to see if they would be interested to participate and whether they are eligible (based on eligibility criteria for healthy subjects and based on safety screening). We will follow a phone script and email for recruitment for healthy subjects. We will respond to email requests for info and include screening form attached.

Given that mid-way study, we have trouble bringing back healthy participants who have participated previously in protocol 64623, we need to recruit new people from general population in Atlanta. We will use flyers to recruit more people. We will post these flyers in different locations around Atlanta area (like in restaurants, college, Marta stations etc). We will need to conduct the IQ test and color blindness prior their main visit to the hospital. Healthy controls should match ASD patients with IQ and race. We are adding race so that samples from both groups stay matched as much as possible.

We have already conducted the total number of patients for this study. The average IQ of ASD patients is 98.39 and the standard deviation is 16.28. The race ratio for ASD is 82% white, 12.5% African American and 6% more than one race,

Accordingly, we are adding a new informed consent and another inclusion criterion for this separate group of healthy subjects (labeled II). The inclusion criteria will include Caucasian race and IQ range between 70 and 115.

The reason that we are adding Caucasian to the inclusion criteria for this new set of healthy subjects is that we have already 2 or 3 contacts from the previous study who are African American and who are interested to participate. This will make approximately 10% of the healthy subject's sample if we were able to recruit 30 total.

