### **Randomization and blinding**

**Clinical trial for ASD subjects:** The trial will be a double-blind, placebo-controlled, several doses of oxytocin, within subject design study. Patients will undergo 4 clinical visits (in addition to a first pre-clinical visit) during which they receive 12 puffs (6 in each nostril) of 8IU total, 24IU and 48IU oxytocin (syntocinon) and placebo (assigned randomly). The placebo will contain the same ingredients as syntocinon, except the active molecule oxytocin. This is essential for making sure that the patient does not recognize the type of treatment he is receiving. Hence, both patients and the experimenter will be blind to the type of the treatment administered.

The pharmacy IDS of Emory will be in charge of the randomization sequence and one of the staff members of the team (who is not involved in testing procedures) will be de-blinded.

We will break the blind after testing 25 patients with ASD to check the results half-way for a mid-point analysis. The mid-point analysis will focus on measures where effect sizes are anticipated to be large enough that the risk of false positives is minimal. We are expecting larger effect size on some measures and therefore we break the blind for those measures to be analyzed and published. Additional data on these measures will continue to be collected and we will attempt to publish the combined analysis at the end to avoid publication bias.

However, the data collection will continue until a sample size equal to 50. Given that we are facing challenges with ASD recruitment and that the study requires the participation in 5 long visits, it is possible that the study will stop at N=30 or 40, in case the PI was not able to recruit more ASD. We also expect dropouts after recruitment. We believe that we will be able to test 30 patients with ASD.

It is possible that this project will be funded by other grant funds which will allow adding more participants (more 50 ASD). In this case, the PI will submit an amendment accordingly.

**Healthy subjects:** There will be only one clinical visit for healthy subjects and they will all receive placebo spray (12 puffs, 6 per nostril). The study will be conducted in a single-blind design. The PI is aware that the subject is receiving placebo. However, the participant will be told that he might

receive oxytocin or placebo. This is important in order to control for the placebo effect on behavior and brain activity.

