### **Statistical analysis:**

Power analysis (using G power 3.1 software) shows that a sample size of 50 subjects with ASD receiving 4 different treatments is needed to reliably detect (95% power) effect sizes small or larger (Cohen's  $d=0.2$ ) on one measure. In this study, we expect to find small to medium size effects of oxytocin inhalation on behavioral measures (based on previous meta-analysis of Bakermans-Kranenburg and Van I Jzendoorn. 2013). Authors found a combined effect size of  $d=0.32$  (95% confidence interval: 0.18-0.47). As mentioned above, we are planning to break the blind with  $N=25$  ASD subjects for a mid-way analysis, which is sufficient to detect effect sizes between medium and small (Cohen's  $d=0.3$ ). We expect larger effect sizes on measures of brain

activity (BOLD activity and functional connectivity). Therefore, these measures will be mainly analyzed during the mid-way analysis for potential publications. Of note, we are also planning to publish the combined analysis with the total number of subjects on the measures that were published mid-way to avoid any publication bias.

For healthy subjects, we need at least 30 subjects receiving on treatment to reliably detect (95% power) the differences between social and non-social conditions or emotional faces versus neutral faces in the aims above with an effect size between small and medium (Cohen's  $d=0.35$ ).

When comparing healthy subjects to patients with autism (placebo administration only), the above numbers are sufficient to reliably detect small effect sizes between groups (Cohen's  $d=0.2$ ) for one measure.

The PI will submit an annual report to the IRB and address whether the study is safe and whether it is appropriate to continue. This report will include compliance, review of eligibility, treatment review, summary of responses, survival, adverse events and safety monitoring rules.

Given that we do not expect serious adverse events and we are investigating the effects of this hormone on brain activity and behavior, we do not expect an early stopping.

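### The 95% power is tied to 50 ASD patients and at least 30 controls, but other current sections work with 30 or 40 patients and with either 20 or 30 controls, and power is not restated at those numbers

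*Combined protocol and SAP*

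**What the plan says.** **Numbers behind the power statement.** The Statistical analysis section says that "a sample size of 50 subjects with ASD receiving 4 different treatments is needed to reliably detect (95% power) effect sizes small or larger", with the effect given as Cohen's d = 0.2 on one measure. For controls it says "we need at least 30 subjects receiving on treatment to reliably detect (95% power) the differences between social and non-social conditions", at d = 0.35. For ASD on placebo against controls it calls the same numbers sufficient for d = 0.2, without giving a power level. For the mid-way look it says N = 25 is enough for d = 0.3, again without a power level.

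**Targets.** Participant selection repeats the sizes: "50 ASD between the ages of 18 and 45 will participate in this study", with 30 healthy controls.

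**Expectations.** Randomization and blinding keeps 50 as the point at which data collection ends, but says the study may stop at 30 or 40 and that dropouts are expected. It adds: "We believe that we will be able to test 30 patients with ASD". The closing paragraphs of the eligibility criteria, under Participant selection, say: "We expect to recruit at least 30 patients with autism and 20 healthy controls". They also expect patients to drop off because of the five visits.

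**Later text.** Healthy subjects screening, written mid-study, says "We have already conducted the total number of patients for this study" but gives no number. It treats a total of 30 controls as conditional on recruitment succeeding.

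No section recomputes power at 30 or 40 patients or at 20 controls, gives a dropout rate, or inflates the sample for dropout.

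**The concern.** A power statement describes one sample size. Here it is made at 50 and 30, while the same document names 30 patients as achievable and 20 controls as the recruitment expectation, and 20 is below the minimum the power section says is needed. All of these sections are current text, not an amendment history.

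The plan distinguishes differences between oxytocin doses from differences between any dose and placebo, so null dose contrasts will have to be interpreted. A reader with only the Statistical analysis section would set such a result against a 5% chance of missing the stated effect. At the smaller numbers that chance is larger, and the plan does not say by how much.

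**Working it through.** **Inputs from the documents.** ASD: 50 (power section and target), 30 or 40 (possible stop), 30 (believed achievable). Controls: 30 (power section, target, and conditionally in Healthy subjects screening), 20 (eligibility section). Four within-subject conditions. Labelled effects: d = 0.2 (ASD), 0.35 (controls), 0.2 (between groups).

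**Assumed, because not stated.** Two-sided alpha 0.05 for t-tests, sphericity for the ANOVA, and a within-subject correlation ρ of 0.5 where one is needed.

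**Step 1. Try to reproduce the plan's own figure.** For a one-group repeated-measures ANOVA with m = 4 conditions, λ = f²·N·m/(1−ρ), with df 3 and 3(N−1). Converting d = 0.2 to f = 0.1 gives λ = 0.01 × 50 × 4/0.5 = 4.0, and power is 35%, not 95%. 95% would need N = 216, or ρ of about 0.89 at N = 50. A paired t-test at d = 0.2 and N = 50 has 28%. Entering 0.2 directly as f gives λ = 16 and 92.7% power, close to the plan's figure, so the labelled d may really be an f. Likewise, a paired t-test at d = 0.35 with 30 controls has 46%, whereas reading 0.35 as f gives 95.9%. Between groups, d = 0.2 at 50 versus 30 has 14%.

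**Step 2. Set the effect-size question aside.** Take the 95% as true at the plan's sizes, solve for the noncentrality that makes it so, and rescale to the other sizes. For the ANOVA the result does not depend on which f and ρ are used, because only λ enters and λ is proportional to N.

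*Four-condition ANOVA, ASD.* 95% at N = 50 needs λ = 17.63.
- N = 40: λ = 17.63 × 40/50 = 14.11, power 88.8%.
- N = 30: λ = 17.63 × 30/50 = 10.58, power 76.6%.

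*Paired t-test, ASD (one dose against placebo).* Noncentrality is d_z√N, and 95% at N = 50 needs d_z = 0.520.
- N = 40: 0.520 × √40 = 3.29, power 89.4%.
- N = 30: 0.520 × √30 = 2.85, power 78.6%.

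*Control-only contrast, paired t-test.* 95% at n = 30 needs d_z = 0.681.
- n = 20: 0.681 × √20 = 3.05, power 82.4%.
- n = 30: no loss.

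*Between groups, two-sample t-test.* Noncentrality is d√(n₁n₂/(n₁+n₂)). The plan states no power level here, so 95% at 50 versus 30 is only a reference point. It needs d = 0.843, since 0.843 × √18.75 = 3.65.
- 30 versus 20: 0.843 × √12 = 2.92, power 81.6%.
- 30 versus 30: 0.843 × √15 = 3.26, power 89.4%.

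**Step 3. Detectable effect at 95% power.** Paired d_z rises from 0.520 (N = 50) to 0.681 (N = 30), a factor of 1.31. In the four-condition ANOVA with ρ = 0.5, f rises from 0.21 to 0.27.

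**The case against.** The strongest defence is that the plan discloses the possible shortfall. It says openly that recruitment may stop at 30 or 40, and it words the power section as what is needed, not as what any achieved sample will deliver. The figure of 30 patients in the eligibility section is a floor, and 50 remains the target. For controls, two sections work with 30, and one of them was written after a new recruitment route had been opened. The plan also calls N = 25 sufficient for d = 0.3, expects d = 0.32 for behaviour, and expects larger effects on the brain measures that are the primary outcomes of Aims 1 to 3. Comparisons of brain function with controls are described as exploratory or secondary.

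Most of this stands, and it rules out a tempting stronger reading: that the trial is known to have ended with 30 patients and 20 controls. The documents do not show that. The statement that patient testing is complete carries no number, and 20 controls is one of two figures in the text. Nor can a reader infer that the primary imaging comparisons are underpowered. The effects expected there are said to be larger, but no size is given, so adequacy is neither shown nor refuted.

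The defence does not supply a power figure at the numbers the plan itself calls realistic. Disclosing that the sample may be smaller does not say what power remains, and the N = 25 statement has no power level attached. The two control numbers still need reconciling.

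**Conclusion.** The inconsistency is real and needs correcting. Accepting the plan's 95%, the chance of missing the same effect in the four-condition comparison rises from 5% to about 11% at 40 patients and 23% at 30. For a control-only contrast it rises to about 18% at 20 controls and is unchanged at 30. These figures rest on two-sided alpha 0.05 and, for the ANOVA, sphericity. They allow for no dropout beyond the numbers shown.

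A reader might also infer that reaching 50 and 30 would restore 95% power. The documents do not support that. Step 1 shows that the figures for 50 patients and 30 controls do not reproduce at the labelled d values unless the within-subject correlation is very high, and the plan states no correlation. No such correlation can rescue the between-group statement. The loss from smaller numbers therefore comes on top of a starting figure that is itself unsupported, and both should be repaired in the same sentences.

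**What to change.** 1. State one number per group in Healthy subjects screening, Randomization and blinding, Participant selection (including the eligibility paragraphs) and Statistical analysis. For ASD, use the number actually tested, which the plan says is final but does not give. For controls, choose and state one number in place of both 20 and 30.
2. In Statistical analysis, replace the 95% statements with power, or the detectable effect, recomputed at those numbers for the four-condition repeated-measures test and for the between-group test. State alpha, sidedness, the assumed within-subject correlation, any sphericity correction, and whether the effect is d or f.
3. Say whether the numbers are recruited or analysed, and show the dropout allowance if they are recruited.
4. Do not keep the 95% by labelling it as applying to 50 and 30.

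This costs text and a short recalculation. It changes no procedure or design feature. The stated power, or the detectable effect, will look less favourable than it does now.
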